# 9.2.7. Exposure to Standard of Care (SOC)

The following parameters will be derived per type of SOC (nintedanib, pirfenidone and neither):

- Duration of SOC= last dose of SOC first dose of SOC + 1 day
- Compliance to SOC (%) = 100 x (number of SOC tablets actually used) / (number of SOC tablets that should have been used in the study).
   Where the number of SOC tablets is to be calculated based on the total study duration (from first dose of IP to last contact).

Summary tables by treatment, type of SOC will be provided for these two parameters.

A frequency table per treatment group, summarizing the SOC intake during the study, of the number and percentage of subjects with the following:

- Baseline SOC pirfenidone:
  - Stable dose until study end date
  - Reduced dose at least once
  - Temporarily stopped at least once
  - Permanently stopped and started nintedanib
  - Permanently stopped (without starting nintedanib)
- Baseline SOC nintedanib:
  - Stable dose until study end date
  - Reduced dose at least once
  - Temporarily stopped at least once
  - Permanently stopped and started pirfenidone
  - Permanently stopped (without starting pirfenidone)
- Baseline SOC neither:
  - Stable until study end date
  - Started nintedanib or pirfenidone and permanently stopped (without restarting other SOC)
  - Started nintedanib or pirfenidone and temporarily stopped (i.e. period without any SOC) at least once
  - Started nintedanib or pirfenidone and continued until study end date (includes subjects that switch SOC without temporary stop)

Note: these categories should be counted in a worst-case manner i.e. a subject appears only once in one of the categories (in the order as specified above with "permanent stop" or "starting SOC" as the worst cases).

Additionally, a frequency table of the type of switch with the reasons for switching SOC will be provided per treatment group.

A frequency table describing the doses taken of Pirfenidone and Nintedanib per treatment group will also be created.

Patient-years exposure to each SOC by treatment group and stratum and overall will be provided.

A frequency table, summarizing SOC intake prior (e.g. Currently taking Pirfenidone; Never took Nintedanib, ...) to the study by treatment group and stratum and overall will be created.

In addition, a listing will be provided of the subjects who had any change in SOC medication (pirfenidone, nintedanib or neither) during the treatment period compared to baseline e.g. switching between nintedanib and pirfenidone, starting pirfenidone/nintedanib, stopping pirfenidone/nintedanib, down-titration or up-titration of pirfenidone/nintedanib. All SOC therapy records are to be included.

In addition, Kaplan-Meier tables and graphs will be created for the time from first dose of IP to switch of SOC, where a switch in SOC is defined as:

- switching from nintedanib to pirfenidone or vice versa for those in the 'nintedanib' or 'pirfenidone' strata,
- starting nintedanib or pirfenidone, for those in the 'neither' stratum.

Furthermore, for those in the 'pirfenidone' or 'nintedanib' stratum, a Kaplan-Meier curve and table will be provided for the time to discontinuation of the SOC they started on.

For the neither stratum, a tabulation of the number of subjects (%) by reason for not taking Pirfenidone and Nintedanib.

A listing of COVID-19 related SOC intake changes will be provided.

Heterogeneity between countries (and/or regions) will be investigated.

If a high number of subjects switching SOC are observed in a blinded fashion during the course of the study, more descriptions may be added to further investigate the patterns over time. Details will then be added to this SAP before unblinding for the final analysis.

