4.5.3.2. Prior and Concomitant Medications

Prior therapy

Prior therapy taken up to 12 weeks prior to and during the screening period, and pirfenidone and nintedanib taken any time prior to and during the screening period will be recorded after signing of the ICF, at Visit 1.

Concomitant therapy

Should any treatment other than the IMP be used during the course of the study, the name of the therapy, the dosage, the route, the reason for therapy, and the start and stop dates of administration must be recorded until the last visit. For subjects receiving oxygen, the volume administered per minute will also be recorded at each visit.

Concomitant therapies taken for the long-term treatment of pre-existing conditions can continue during the study, provided they are in accordance with the in- and exclusion criteria (see Sections 4.5.1 and 4.5.2, respectively). It is required that the use of these medications should have been stable from 4 weeks prior to screening and during the screening period (at the investigator's discretion). For nintedanib and pirfenidone, subjects need to have received a stable dose for at least two months prior to screening and during screening; stable being defined as the highest dose tolerated by the subject during those two months.

In case additional concomitant medication needs to be administered or dose adjustments for pre-existing conditions need to be performed during the study, the benefit-risk to the subject should be carefully assessed and consideration given to the timing of any necessary introduction of new medications.

The following therapies are prohibited during the course of the study and within 4 weeks prior to screening, because of lack of benefit or suggestion of harm in IPF: warfarin, imatinib,

ambrisentan, azathioprine, cyclophosphamide, cyclosporine A, bosentan, methotrexate, sildenafil (except occasional use), prednisone at steady dose >10 mg/day or equivalent.

If during the study, the subject's condition necessitates the use of one of the abovementioned medications (excluding high-dose steroids), the use of IMP should be interrupted until resolution or stabilization of this condition, preferably after consultation with the CRO medical monitor (as per study contact list) or sponsor's study physician (if the former is not available).

Precautions with concomitant medication known to prolong the QT interval

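### SAP 9.2.7 counts expected standard-of-care tablets over the whole study, so a permitted stop or switch scores as poor compliance; standard-of-care duration has no stated on-study start.

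*SAP*

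**What the plan says.** SAP 9.2.7 defines two parameters, to be derived separately for nintedanib, pirfenidone and neither, and tabulated by treatment and type of SOC.

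- **Compliance** is 100 times tablets used over tablets that should have been used. The next sentence fixes the time base: the count is "calculated based on the total study duration", which the SAP spells out as first IP dose to last contact. No exception is given for a subject who stops, switches or starts SOC during the study.
- **Duration** begins "Duration of SOC= last dose of SOC", less the first SOC dose, plus one day. The text does not say whether the first dose is the first ever, the first recorded, or the first on study.

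The section also promises "Patient-years exposure to each SOC by treatment group and stratum and overall will be provided", again without a stated start.

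SAP 6.5 has two definitions of last contact, one that uses the vital status form and one that does not. SAP 9.2.7 names neither. By contrast, SAP 9.2.2 states for time in study that vital-status data are left out.

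The protocol expects SOC to change: the note to Table 1 in Section 6.7 says so, and SAP 9.2.7 has categories for reductions, temporary and permanent stops, switches and new starts. Protocol 4.5.3.2 says that "pirfenidone and nintedanib taken any time prior to and during the screening period will be recorded". Inclusion criterion 6.1 requires at least two months of stable use before screening for subjects on either drug.

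**The concern.** Compliance should compare what was taken with what was prescribed. A subject taken off nintedanib halfway through was not meant to take it afterwards, yet the stated denominator keeps counting. The result mixes adherence with persistence under the label of adherence.

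For duration, every subject in the two SOC strata was on the drug before the study, and that history is recorded. Without an anchor, a programmer could start the clock before randomization.

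SAP version 2 keeps an abbreviated set of analyses, partly to understand the result. It drops the sensitivity analyses for SOC changes (9.3.2.2.8) and the Kaplan-Meier analysis of time to first switch (listed in 9.1). The 9.2.7 summaries are therefore among the remaining descriptions of background therapy by arm. If stops differ between arms, the arm with more stops would look less compliant even if all subjects took what they were prescribed.

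**Working it through.** The documents give no numerical result for either parameter, so there is no figure to reproduce. The check applies the two formulas as written to example subjects.

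**Inputs.** On-study time is 52 weeks (364 days) to about 132 weeks (924 days), from SAP 2.3. Prior SOC use is at least two months, taken as 62 days (inclusion criterion 6.1). Longer prior use is an assumption; five years (1826 days) is a rough ceiling if SOC starts after diagnosis, since inclusion criterion 4.1 requires diagnosis within five years. A constant daily tablet count is assumed, so tablets cancel to days.

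**Compliance, all prescribed tablets taken.** Formula: 100 × days on that SOC / days from first IP dose to last contact.

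| Subject | Starting drug | Second drug, if scored |
|---|---|---|
| Stops at day 182 of 364 | 182/364 = 50% | none |
| Switches at day 182 of 364 | 182/364 = 50% | 182/364 = 50% |
| Switches at day 91 of 364 | 91/364 = 25% | 273/364 = 75% |

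The same fractions of 924 days give the same percentages. With expected tablets limited to prescribed days, each entry is 100%.

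**Last contact.** A compliant subject withdraws at day 182. If the vital-status date counts and falls at day 364, compliance is 182/364 = 50%; at day 924 it is 182/924 = 20%. Protocol 4.5.4 collects vital status for withdrawn subjects around the time the last subject reaches Week 52, so such gaps can arise.

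**Duration, if the first recorded dose is used.** Formula: (prior days + on-study days) / on-study days, for a subject on SOC throughout.

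| Prior use | 364 days on study | 924 days on study |
|---|---|---|
| 62 days (guaranteed) | 426/364 = 1.17 | 986/924 = 1.07 |
| 730 days (assumed) | 1094/364 = 3.01 | 1654/924 = 1.79 |
| 1826 days (assumed) | 2190/364 = 6.02 | 2750/924 = 2.98 |

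Started at the later of first SOC dose and first IP dose, the same subject has 364 or 924 days.

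**Effect on an arm mean (illustration).** If a proportion p stops, stops fall evenly over the year and adherence is perfect until then, mean compliance is 100 × (1 − p/2). For p of 10%, 20% and 30% that is 95%, 90% and 85%. The documents give no stopping rates.

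**The case against.** **Low stakes.** SAP 9.2 allows no testing or p-values for subject information. The primary estimand (SAP 4) uses the data regardless of SOC changes, and even the dropped SOC sensitivity analyses used their own 75%-of-time rule. Stops, switches and reasons appear in the 9.2.7 frequency tables, a listing, and a Kaplan-Meier display of time to discontinuation of the starting SOC. All of this stands and limits the point. It does not correct a summary labelled compliance that measures something else.

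**Type of SOC may mean baseline stratum.** A switcher would then be scored once, and someone in the neither stratum who starts a drug late would not be scored on it. This is a fair reading, so the second-drug figures are conditional. The 50% on the starting drug does not depend on it.

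**No SOC pill count is described.** Accountability in Protocol 5.5 covers IMP only. Section 6.4 has subjects record nintedanib intake times only on certain visit days, plus medication changes, and Section 4.5.3.2 records dosage with start and stop dates. If nothing more is collected, compliance on prescribed days would be near 100% by construction and the share of study time on SOC would be the informative quantity. This stands. It argues for reporting that share under its own name.

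**Stronger readings that a reader might infer.** One is that on-study SOC exposure is overstated by years. The text leaves the first dose undefined, does not label duration as on-study, and defers derivation details to a separate document (SAP 1); only two months of prior use is guaranteed. Another is that patient-years are inflated: their construction is not stated. A third is that counting gaps is an error: last minus first dose matches the plan's own convention for IP (Protocol 7.3.5.1; SAP 9.2.6). A fourth is that stops will differ by arm. The roughly two-fold rise in nintedanib exposure in Protocol 4.4 is for simultaneous dosing with 600 mg, the same section reports a smaller interaction when intakes are separated, and no arm-specific stopping rates are given.

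**Conclusion.** The compliance rule is wrong as stated: a permitted stop or switch halfway through gives about 50% on the starting drug for a subject who missed nothing. The second drug also scores about 50% only if each drug taken is scored. The unspecified last-contact date can push a compliant early withdrawal to 50% or, in the 924-day example, 20%.

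For duration, the fault is a missing anchor. If the first recorded dose is used, the value exceeds on-study exposure for every subject in the two SOC strata, by 1.17 times for 52 weeks of continuous use with 62 days of prior use. Larger multiples rest on assumed histories.

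The consequence is confined to the by-arm description of background therapy. No efficacy or safety test depends on either parameter.

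**What to change.** In SAP 9.2.7:

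1. Limit expected tablets to the on-study days on which that SOC was prescribed, at the prescribed dose.
2. Report percent of study time on each SOC as a separate, correctly labelled parameter.
3. Start SOC duration and patient-years at the later of first SOC dose and first IP dose.
4. Use the SAP 6.5 last-contact definition that excludes the vital status form.
5. Do not derive compliance for the neither category, which has no tablets.

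Keep the existing displays of stops and switches.

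The cost is SAP wording and two or three re-derivations from SOC dates and doses. The drawback is that compliance may sit close to 100% and say little if only dates and doses are recorded; percent of time on SOC would then carry the information.

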# 9.3. Efficacy Analyses

This section provides an overview of the efficacy analyses performed for this study.

# 9.3.1. Level of Significance

Given no market authoristation applicaton for ziritaxestat for the treatment of IPF will be submitted anymore, no pooled analyses combining data from both studies will be performed and the below multiplicity adjustment strategy for countries outside US, does not apply. Only abbreviated CSRs per study will be written as explained earlier in this document.

Statistical tests will be done at a 2-sided level. For the analysis of the primary endpoint, to account for the multiple testing due to two doses being compared to placebo, a Bonferroni approach (Hochberg, 1988) will be used with higher priority given to the high-dose group. The primary endpoint will be tested at a 4% level when comparing GLPG1690 600 mg to placebo and a 1% level for GLPG1690 200 mg group versus placebo.

With respect to the multiplicity adjustment for the key secondary endpoints an additional approach was requested by the compared to European Union (EU) countries. For countries outside US and EU, the EU approach will be applied.

#### For

The requested a multiplicity adjustment for the key secondary endpoints within each study. A closed-testing hierarchical approach will therefore be used for each dose group separately. The

key secondary endpoints will be ordered as listed in Section 2.2.2.1 and they will be tested at a 4% level when comparing GLPG1690 600 mg to placebo and a 1% level for GLPG1690 200 mg group versus placebo. In this approach, the first key secondary endpoint in a dose group will only be tested if the primary endpoint for that dose group showed significance. The next one will only be tested if the previous one showed significance. These analyses will be presented in the study CSR. Figure 2 details the testing order within each of the identically designed studies.

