7.1. Determination of Sample Size

To account for multiple testing due to multiple doses, a Bonferroni approach [9] will be applied to the alpha level with higher priority given to the high-dose group. The primary endpoint will be tested at a 4% level when comparing GLPG1690 600 mg to placebo and a 1% level for GLPG1690 200 mg group versus placebo.

Denoting Δ_{600} and Δ_{200} , the true treatment differences of the two GLPG1690 treatment groups with placebo, and assuming a common standard deviation (SD) on the 52 weeks decline in FVC of 275 mL, the probabilities that 0, 1, or 2 treatment comparisons with placebo are statistically significant, are presented in Table 2. The family-wise error rate is protected at 5% using the Bonferroni procedure. The so-called disjuncture power of the study is the probability that 1 or 2 hypotheses are rejected and is displayed in the right-most column of Table 2.

A meta-analysis of the seven placebo-controlled studies that have been conducted on nintedanib, pirfenidone, and pamrevlumab has revealed that the treatment effect at 52 weeks is estimated to be approximately 119 mL in a treatment-naïve population, the effect observed with nintedanib alone is similar (112 mL) [32]. Little information is available on the expected treatment effect of GLPG1690 in addition to pirfenidone or nintedanib. Table 2 gives an overview of the power for different scenarios for the overall treatment effect in the population of subjects on standard of care (either pirfenidone or nintedanib, or neither pirfenidone nor nintedanib).

Since the linear-slope model on the annual rate of decline in FVC accounts for missing data, the number of subjects randomized and the number of subjects included in the model is expected to be equal. An equal number of 250 subjects will be randomized to each treatment group to have at least 80% power to show a significant effect assuming the 600-mg group has a treatment effect of at least 80 mL in the overall population of treatment naïve and patients on standard of care.

Table 2: Probability of Statistical Significance of 0, 1, or 2 Treatment Comparisons With Placebo

mL	0 Successful	1 Successful	2 Successful	Power
$\Delta_{600}=80$ $\Delta_{200}=80$	6.8%	23.4%	69.9%	93.2%
$\Delta_{600}=80$ $\Delta_{200}=60$	10.1%	46.9%	43.0%	89.9%
$\Delta_{600}=80$ $\Delta_{200}=20$	11.5%	84.4%	4.1%	88.5%
$\Delta_{600}=80$ $\Delta_{200}=0$	11.2%	88.0%	0.7%	88.8%
$\Delta_{600}=90$ $\Delta_{200}=60$	5.1%	51.1%	43.8%	94.9%

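### The within-study testing scheme controls family-wise error at 5%, but the alpha of a dose whose whole chain is rejected is not passed to the other dose, so some power for 200 mg is given up without need

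*SAP*

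**What the plan says.** For the primary endpoint, SAP 9.3.1 splits alpha between the doses: "tested at a 4% level when comparing GLPG1690 600 mg to placebo and a 1% level for GLPG1690 200 mg group versus placebo". Tests are two-sided ("Statistical tests will be done at a 2-sided level"). Protocol 7.1 and 7.3.4 give the same split, and Protocol 7.1 states: "The family-wise error rate is protected at 5% using the Bonferroni procedure".

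For the key secondary endpoints, the within-study approach in SAP 9.3.1 sets up one ordered chain per dose: "A closed-testing hierarchical approach will therefore be used for each dose group separately". The levels stay the same along the chain: "they will be tested at a 4% level when comparing GLPG1690 600 mg to placebo and a 1% level for GLPG1690 200 mg". Each step depends only on the same dose: "the first key secondary endpoint in a dose group will only be tested if the primary endpoint for that dose group showed significance", and so on down the list. The order is disease progression, respiratory-related hospitalization, SGRQ total score.

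A second scheme, for countries outside the US, tests the key secondaries on data pooled from the two studies, and only if both primaries are significant (Protocol 7.3.4, SAP 9.3.1). SAP version 2.0 says this pooled strategy no longer applies, which leaves the within-study scheme.

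Neither document contains visible text that raises either level once the other dose's chain is complete. SAP Figure 2, which shows the testing order, is not visible in the copy reviewed.

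**The concern.** Each dose has four hypotheses tested in order at a fixed level. If all four are rejected for 600 mg, its 4% has no further use. A Bonferroni-based graphical procedure would hand that 4% to 200 mg, whose chain could then be tested at 5%. Under the plan, 200 mg still faces 1% even when 600 mg has won on everything.

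What is at stake is the chance of a confirmed result for the lower dose. The protocol treats that dose as confirmatory: the objectives name both doses, and section 4.2.1 puts the anticipated therapeutic range between them.

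**Working it through.** **Inputs (Protocol 7.1).** SD 275 mL, 250 subjects per arm, levels 4% and 1% two-sided, effect sizes from Table 2. The two dose-placebo statistics share the placebo arm, so with equal arms their correlation is 0.5.

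**Standard error and critical values.** SE = 275 × √(2/250) = 24.60 mL. Critical values are z = 2.054 (4%), 2.576 (1%) and 1.960 (5%).

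**Protocol Table 2, with fixed 4%/1% tests and no transfer.**

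| 600 / 200 mg effect (mL) | Both significant: printed | Computed | At least one: printed | Computed |
|---|---|---|---|---|
| 80 / 80 | 69.9% | 70.1% | 93.2% | 93.4% |
| 80 / 60 | 43.0% | 43.0% | 89.9% | 90.0% |
| 50 / 50 | 21.9% | 21.5% | 56.1% | 57.0% |
| 0 / 0 | 0.3% | 0.2% | 4.8% | 4.8% |

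The table reproduces. Passing the 4% on directly after the 600 mg primary would give 82.2% for both at 80/80, so the printed figures include no transfer at that step. Table 2 covers only the primary tests and says nothing about a transfer after a full chain; for that, the SAP text is the evidence.

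**Does an end-of-chain transfer keep 5%?** There are two cases.
- Both chains contain a true null hypothesis. A transfer needs the other chain to be fully rejected, which would already include a false rejection. The first false rejection therefore happens at 4% in one chain or 1% in the other: at most 4% + 1% = 5%.
- Only one chain contains a true null. The first true null in that chain is tested at no more than 5%.

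Family-wise error stays at or below 5%, and no hypothesis is tested at a lower level than in the plan.

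**Marginal power of the primary test**, Φ(effect/24.60 − z):
- 200 mg, 80 mL: 75.1% at 1%, 90.2% at 5%
- 200 mg, 60 mL: 44.6% at 1%, 68.4% at 5%
- 600 mg, 80 mL: 88.5% at 4%, 90.2% at 5%

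**Upper bound on the gain for 200 mg.** Suppose the three 600 mg key secondaries always succeed once the 600 mg primary does. Then

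P(200 mg significant) = P(p200 < 1%) + P(p600 < 4%, p200 < 5%) − P(p600 < 4%, p200 < 1%).

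- 80/80: 75.1 + 82.2 − 70.1, which is 87.1% before rounding of the terms; gain 12.0 points.
- 80/60: 44.6 + 64.5 − 43.0, which is 66.0% before rounding; gain about 21 points.

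**Between the bounds.** Let q be the chance that all three 600 mg key secondaries are rejected given its primary. The documents do not give q. It is an assumption here, and is taken as independent of the 200 mg result.

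| q | 200 mg power, 80/80 | 200 mg power, 80/60 |
|---|---|---|
| 0 (plan) | 75.1% | 44.6% |
| 0.1 | 76.3% | 46.7% |
| 0.3 | 78.7% | 51.0% |
| 0.5 | 81.1% | 55.3% |
| 0.8 | 84.7% | 61.7% |
| 1 | 87.1% | 66.0% |

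**Reverse path.** If the 200 mg chain completes and its 1% passes to 600 mg, the gain at 80 mL is at most 90.2 − 88.5 = 1.7 points.

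**The case against.** The split is deliberate and valid. The plan gives 600 mg priority, states a power target only for that dose (at least 80% at 80 mL), and meets it with 88.5%. A simpler procedure is easier to explain, and no power target for 200 mg is missed. This stands as a reason to call the change optional. It is not a reason to prefer the plan's scheme, since the transfer leaves the 4%/1% start and the priority for 600 mg untouched.

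A reader might infer that 200 mg loses about 15 points at 80 mL (75.1% against 90.2%) or about 24 at 60 mL (44.6% against 68.4%). The documents do not support that. Those pairs compare 1% with 5% as if 200 mg always received the extra alpha. It would receive it only after four 600 mg rejections at 4% within one study. The plan itself suggests this is demanding: it wanted to pool two studies to raise the chance of detecting effects on the key secondaries, some of which it describes as rare events. At q = 0.1 the gain is 1.2 points (80/80) or 2.1 points (80/60).

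A reader might also infer that the SAP should be amended now. It should not. Version 2.0 was written after the studies were halted, no marketing application will follow (SAP 1), and part of the study team has been unblinded (SAP 2.7). Loosening a confirmatory rule at that stage would not be credible.

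Finally, SAP Figure 2 and Protocol Figure 4 cannot be seen, so the absence of a transfer rests on the text. The text sets the levels without condition.

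**Conclusion.** The point holds as a limited efficiency remark. The within-study scheme is valid but dominated, because a completed chain's alpha goes unused. For the 200 mg primary test the avoidable loss lies between 0 and about 12 points at 80/80 mL, and between 0 and about 21 points at 80/60 mL. Where it falls depends on the chance that all three 600 mg key secondaries succeed, which the documents do not state. Later steps of the 200 mg chain would also be tested at 5%, but no figures exist to size that gain.

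A reader might take this as a type I error fault. It is not: Table 2 shows 4.8% under the global null, and the recomputation agrees.

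The figures rest on the normal approximation, SD 275 mL, 250 per arm and correlation 0.5. The change is optional and has little practical effect on this trial, which stopped for lack of efficacy.

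**What to change.** For a plan of this design, before unblinding, add to the within-study part of SAP 9.3.1:

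*If the primary and all three key secondary hypotheses for one dose are rejected within a study, that dose's alpha passes to the other dose, whose chain is then tested in the same order at two-sided 5%.*

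Add the matching arrow at the end of each chain in SAP Figure 2. If that figure already shows a transfer, align the text with it instead.

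Do not add the sentence to the pooled scheme for countries outside the US in Protocol 7.3.4. There the key secondaries use data from both studies and depend on both primaries, so it is unclear whether completing a pooled chain would reopen a single study's 200 mg primary, and the 5% bound above was not shown for that case. Do not apply the rule retrospectively to CL-303 or CL-304.

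Cost: one sentence and a figure edit. No patients are needed and the initial split does not change. Because the within-study adjustment was made on request, the party that asked for it would probably need to agree.
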